6.3.2. Blinding

This will be a double-blind study with respect to allocation of GSK3858279 or placebo to participants and the following will apply.

- The investigator or treating physician may unblind a participant's intervention assignment **only in the case of an emergency** OR in the event of a serious medical condition when knowledge of the study intervention is essential for the appropriate clinical management or welfare of the participant as judged by the investigator.
- The interactive voice response system (IVRS)/ interactive web recognition system (IWRS) will be programmed with blind-breaking instructions. In case of an emergency, the investigator has the sole responsibility for determining if unblinding of a participant's intervention assignment is warranted. Participant safety must always be the first consideration in making such a determination. If the investigator decides that unblinding is warranted, the investigator should make every effort to contact GSK prior to unblinding a participant's intervention assignment unless this could delay emergency treatment of the participant. If a participant's intervention assignment is unblinded GSK must be notified within 24 hours after breaking the blind. The date and reason that the blind was broken must be recorded in the source documentation and CRF, as applicable.

- If GSK personnel are not contacted before the unblinding, the investigator must notify GSK as soon as possible after unblinding, but without revealing the intervention assignment of the unblinded participant, unless that information is important for the safety of participants currently in the study.
- The date and reason for the unblinding must be fully documented in the CRF
- A participant will be withdrawn if the participant's intervention code is unblinded by the investigator or treating physician. The primary reason for discontinuation (the event or condition which led to the unblinding) will be recorded in the CRF. The participant will be followed up for safety monitoring if treatment was received.
- GSK's Safety and Medical Governance (SMG) staff may unblind the intervention assignment for any participant with an SAE. If the SAE requires that an expedited regulatory report be sent to one or more regulatory agencies, a copy of the report, identifying the participant's intervention assignment, may be sent to investigators in accordance with local regulations and/or GSK policy.

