7.2. Discontinuation of Study Intervention

A participant will be permanently withdrawn from study treatment if any of the following symptoms or abnormalities occur, and an investigation will be carried out as described below. After withdrawal of treatment (under these conditions), where possible participants should complete the Early Withdrawal visit and be followed up for safety monitoring. Study medications will be discontinued and the participant withdrawn from the study in the event of any of the following:

[figure not shown]
- All serious infections
- Severe or serious hypersensitivity reactions, including anaphylaxis
- If the liver chemistry stopping criteria (Section 7.2.1) or QTc stopping criteria (Section 7.2.2) are met.
- Other serious or severe adverse events, at the discretion of the Investigator, after consultation with the GSK Medical Monitor.

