7.3. Participant Discontinuation/Withdrawal from the Study

- A participant may withdraw from the study at any time at his/her own request or may be withdrawn at any time at the discretion of the investigator for safety, behavioural, compliance or administrative reasons. This is expected to be uncommon.
- At the time of discontinuing from the study, if possible, an early discontinuation visit should be conducted, as shown in the SoA. See SoA for data to be collected at the time of study discontinuation and follow-up and for any further evaluations that need to be completed.

- The participant will be permanently discontinued both from the study intervention and from the study at that time.
- If the participant withdraws consent for disclosure of future information, the sponsor may retain and continue to use any data collected before such a withdrawal of consent.
- If a participant withdraws from the study, he/she may request destruction of any samples taken and not tested, and the investigator must document this in the site study records.

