12.4. Appendix 4: Study Phases and Treatment Emergent Adverse Events

12.4.1. Study Phases

Assessments and events will be classified according to the time of occurrence relative to the start date of the study treatment.

Study Phase	Definition
Pre-Treatment	Date/Time < Study Treatment Dose Date/Time (Period 1)
On-Treatment	Study Treatment Dose Date/Time (Period 1) ≤ Date/Time

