12.4.2. Treatment Emergent Flag for Adverse Events

Flag	Definition
Treatment Emergent	
 • If the AE is on-treatment, then the AE is treatment emergent. • Refer to Section 12.6.1 for period definitions.

NOTES:

- Time of study treatment dosing and start/stop time of AEs should be considered, if collected.

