12.6. Appendix 6: Derived and Transformed Data

12.6.1. General

Multiple Measurements at One Analysis Time Point	

 Mean of the measurements will be calculated and used in any derivation of summary statistics but if listed, all data will be presented. Participants having both High and Low values for Normal Ranges at any post-baseline visit for safety parameters will be counted in both the High and Low categories of “Any visit post-baseline” row of related summary tables. This will also be applicable to relevant Potential Clinical Importance summary tables. 	
Study Period	

 The start date of Period [1/2/3] is the dosing Day 1 date for that period. The end date of Period [1/2] is the Day -1 date for the subsequent period. The end date for Period 3 and Period[1/2] if no subsequent period follows, will be the final follow up visit date, or if applicable, study withdrawal date, whichever date is earlier. 	
Study Day / Period Day	

 Study day is derived with respect to the very first dose date (Period 1): 
 Ref Date = Missing → Study Day = Missing Ref Date < Dose Date → Study Day = Ref Date – Dose Date Ref Date ≥ Dose Date → Study Day = Ref Date – (Dose Date) + 1 Period day is derived with respect to the dose date during that period: 
 Ref Date = Missing → Period Day = Missing Ref Date < Period Start Date → Period Day = Ref Date – Period Dose Start Date Ref Date ≥ Period Start Date → Period Day = Ref Date – (Period Dose Start Date) + 1 	

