12.11.7. Safety Tables

Safety: Tables – All Safety Tables will be presented by Period unless stated otherwise.					
No.	Population	IDS / Example Shell	Title	Programming Notes	Deliverable [Priority]
Adverse Events (AEs)					
3.01.	Safety	AE1xo	Summary of All Adverse Events by System Organ Class and Preferred Term by Period	ICH E3 Present by Period Programming note: For interim analysis present AEs SOCs and PTs which have more than 2 subjects overall per period. i.e. at least two unique subjects in the Total column per period. Include footnote: Note: For interim, only AEs occurring in two or more subjects by period are reported.	IA 1 [1], IA 2 [2], SAC [3]
3.02.	UVB-Safety	AE1xo	Summary of All Adverse Events by System Organ Class and Preferred Term by Period – UVB Participants Only	ICH E3 Present by Period	SAC [1]
3.03.	Safety	AE1xo	Summary of All Adverse Events by System Organ Class and Preferred Term - Overall	ICH E3 Present Placebo, GSK3858279, Total Columns	SAC [1]
3.04.	Safety	AE5A	Summary of All Adverse Events by System Organ Class and Preferred Term and Maximum Intensity by Period	ICH E3	SAC [1]
3.05.	Safety	AE1xo	Summary All Drug-Related Adverse Events by System Organ Class and Preferred Term by Period	ICH E3	SAC [1]
3.06.	Safety	AE5A	Summary of All Drug-Related Adverse Events by System Organ Class and Preferred Term and Maximum Intensity by Period	ICH E3	SAC [1]
3.07.	Safety	AE3	Summary of Non-Serious Drug-Related Adverse Events by Overall Frequency by Period	PLS Requirement	SAC [1]

Safety: Tables – All Safety Tables will be presented by Period unless stated otherwise.					
No.	Population	IDSL / Example Shell	Title	Programming Notes	Deliverable [Priority]
3.08.	Safety	AE15	Summary of Common (>=5%) Non-serious Adverse Events by System Organ Class and Preferred Term (Number of Participant and Occurrences) by Period	FDAAA, EudraCT	SAC [1]
Serious and Other Significant Adverse Events					
3.09.	Safety	AE16	Summary of Serious Adverse Events by System Organ Class and Preferred Term (Number of Participants and Occurrences) by Period	FDAAA, EudraCT Produce if more than 5 SAEs are reported.	SAC [1]
3.10.	Safety	AE3	Summary of Serious Drug-Related Adverse Events by Overall Frequency by Period	PLS Requirement	SAC [1]

Safety: Tables – All Safety Tables will be presented by Period unless stated otherwise.					
No.	Population	IDSL / Example Shell	Title	Programming Notes	Deliverable [Priority]
Laboratory: Chemistry					

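### The SAP ends a withdrawn participant's last period at the withdrawal date, so an adverse event that starts afterwards is treatment-emergent but belongs to no period

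*SAP*

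**What the plan says.** **Period dates.** SAP 12.6.1 starts each period at its infusion date. A period followed by another ends on Day -1 of the next one. A participant's last period ends on the "final follow up visit date, or if applicable, study withdrawal date, whichever date is earlier".

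**Adverse event classification.** SAP 12.4.1 defines on-treatment as "Study Treatment Dose Date/Time (Period 1) ≤ Date/Time", with no upper limit. SAP 12.4.2 then says "If the AE is on-treatment, then the AE is treatment emergent", and for periods adds "Refer to Section 12.6.1 for period definitions".

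**Tables.** The header of SAP 12.11.7 reads "All Safety Tables will be presented by Period unless stated otherwise". Of the adverse event tables 3.01 to 3.10, only 3.03 is overall. It has Placebo, GSK3858279 and Total columns.

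**What happens after withdrawal.** Protocol 7.2 withdraws participants who meet a stopping rule and says that "where possible participants should complete the Early Withdrawal visit and be followed up for safety monitoring". Protocol 6.3.2 withdraws a participant whose code is broken by the investigator or treating physician and says "The participant will be followed up for safety monitoring if treatment was received". On timing, Protocol 7.3 says "The participant will be permanently discontinued both from the study intervention and from the study at that time".

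**Two other SAP rules bear on the point.** SAP 12.7.1 puts the available planned data of withdrawn participants into summary tables and figures unless otherwise specified. The programming note to liver Table 3.23 places events reported in a washout under the last treatment received.

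**The concern.** The period closes at withdrawal, but safety observation may continue. An event that starts in between meets the SAP's definition of treatment-emergent and has no period to be tabulated under. The treatment column is also undefined: in the sequences A/P/P and P/A/A (SAP 5.1) treatment changes from one period to another within a participant, so some rule must link an event to an infusion.

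The gap falls only on participants who stop early, including those stopped for safety. The protocol's risk table (2.3.1) names immune-complex, infection and skin risks, which need not appear before withdrawal. Protocol 4.4 reports serum drug falling below quantification after 8 weeks at this dose, so later onset is plausible. With at most 30 participants, one event can change a table cell.

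**Working it through.** The issue is a date rule, so the check applies it literally and then measures the window it leaves open.

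**1. One illustrative participant.** Days are counted from the first infusion. Assumed: infusions on days 0 and 28, study withdrawal on day 35, and safety contact until day 84 (28 + 56).

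- Period 1 runs from day 0 to day 27.
- Period 2 runs from day 28 to min(84, 35) = day 35.
- On-treatment is any day from 0 onward.

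| Event onset (day) | Treatment-emergent | Period under SAP 12.6.1 | Period if the last one ran to last safety contact |
|---|---|---|---|
| 10 | yes | 1 | 1 |
| 30 | yes | 2 | 2 |
| 35 | yes | 2 | 2 |
| 36 | yes | none | 2 |
| 50 | yes | none | 2 |
| 84 | yes | none | 2 |

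Only onsets after day 35 change.

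**2. Tables touched.** There are ten adverse event tables (3.01 to 3.10) and one is overall (3.03), so 10 - 1 = 9 are by period: 3.01, 3.02 and 3.04 to 3.10. In Table 3.03 the event can be counted under Total, but no general rule assigns it to Placebo or GSK3858279. Listing 16, of all adverse events, is not limited by period.

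**3. Width of the window.** Final follow-up is planned 56 ± 4 days after the last dose (protocol 1.3.1), that is, 52 to 60 days. For withdrawal w days after the last infusion, the time outside any period is at most 56 - w, with range 52 - w to 60 - w. The values of w are assumptions.

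| w (days) | 56 - w | Range |
|---|---|---|
| 1 | 55 | 51-59 |
| 7 | 49 | 45-53 |
| 14 | 42 | 38-46 |
| 28 | 28 | 24-32 |

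These are upper limits. The schedule of activities gives withdrawn participants an Early Withdrawal visit and no separate later schedule, so follow-up to day 56 is not assured for them.

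**4. How many participants.** The plan's own figure reproduces: 24 completers at 20% dropout (protocol 9.2 and 9.2.1) need 24 / (1 - 0.20) = 30, hence 30 - 24 = 6 planned non-completers. That counts dropouts for any reason. It does not count participants with safety follow-up and a new event, and the documents give no figure for those.

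**The case against.** The best case on the other side is that exclusion is inferred. SAP 8.1 selects adverse events by on-treatment status, which has no end. SAP 12.7.1 favours including withdrawn participants' available planned data. No sentence says that an event outside the period dates is dropped. The period-day formula in SAP 12.6.1 has no upper limit either. This stands as far as it goes: the plan leans towards inclusion. But none of these rules says which period such an event belongs to. The period-day formula takes the period as given; in the example, day 50 is later than the start of both periods. The rules need reconciling.

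Second, the SAP does not define the study withdrawal date. If it were recorded as the last safety contact, the gap would close. Protocol 7.3 points to the moment of discontinuation, but the recorded date cannot be confirmed from the documents.

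Third, follow-up under protocol 7.2 is qualified, and 6.3.2 is firm but gives no schedule. This also stands. Follow-up is firmer for liver stopping events, where Appendix 5 lists monitoring until resolution, stabilisation or return to baseline among its required actions.

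A reader might infer that every event found during post-withdrawal follow-up is lost. The documents do not support that. An event that began on or before withdrawal keeps its period even if it is found later, and this will usually include the stopping event itself. Events that start afterwards remain in the listings and can enter the Total of Table 3.03.

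**Conclusion.** The point holds as a reporting gap. Read literally, SAP 12.6.1 and 12.4 make an adverse event with onset after study withdrawal treatment-emergent but give it no period. It then has no place in nine of the ten adverse event tables and no defined treatment column in the tenth. This also sits badly with SAP 12.7.1. The conclusion assumes that the withdrawal date is the date of discontinuation, as protocol 7.3 suggests, and that some safety follow-up takes place after it.

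The number of events affected cannot be derived. The 49 days (45 to 53) illustrate one assumed withdrawal day and are an upper limit. It would be tempting to say that 6 of 30 participants are affected, or that the early termination recorded in the SAP's version history adds to them. Neither follows: planned dropout covers all reasons, and the documents do not say whether participants were still under follow-up when the study was terminated.

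Sample size and the primary PainCart analysis are untouched. The change is still worth making, because the gap falls on early stoppers and costs little to close.

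**What to change.** In SAP 12.6.1, drop the earlier-of-two-dates clause for adverse event assignment. State instead that adverse events starting after study withdrawal are counted under the period and treatment of the last infusion received, through the last safety contact. This extends the logic of the Table 3.23 note to all adverse event tables. Define the study withdrawal date in the same place, and cross-refer from SAP 12.4.2 and 12.7.1 so that the three sections agree. SAP 12.4.1.1 uses the same period dates for concomitant medication, so Table 1.17 should be checked at the same time.

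The cost is a sentence or two in the SAP and a small change to one derivation. Assigning an event needs only its onset date and the infusion dates, so it does not depend on whether a last safety contact date is recorded separately.

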12.6.2. Study Population

Extent of Exposure	

 This is a single dose per period study, the volume of infusion will be recorded, as will the start and stop date/time of infusion. Number of days of exposure to study drug will be calculated based on the formula: Duration of Exposure in Days = Date of Subsequent/Last Dose – (Date of First Dose) +1+ 18*5 Participants who were randomized but did not report a treatment start date will be categorised as having zero days of exposure. 	
Age	

 Birth date will be presented in listings as 'YYYY'. GSK standard IDSL algorithms will be used for calculating age where birth date will be imputed as follows: 
 Any subject with a missing day will have this imputed as day '15'. Any subject with a missing date and month will have this imputed as '30th June'. Calculated based on the screening date Completely missing dates of birth will remain as missing, with no imputation applied. Consequently, the age of the participant will not be calculated and will remain missing. 	
Body Mass Index (BMI)	

 Calculated as Weight (kg) / [Height (m)²] 	

Race Category

• The five high level Food and Drug Administration (FDA) race categories and designated Asian subcategories are:
1. African American/African Heritage2. American Indian or Alaska Native3. Asian
a) Central/South Asian Heritageb) Japanese/East Asian Heritage/South East Asian Heritagec) Mixed Asian Heritage (only required if data exists)4. Native Hawaiian or other Pacific Islander5. White• These categories and subcategories will be summarized along with all combinations of high level categories which exist in the data. All five of the high level race categories and the two Asian subcategories must appear on the display even if there are no participants in a particular category, but combinations that do not exist in the data do not need to be represented. Combinations will be represented as the concatenation of the high level category terms, e.g., "White & Asian." The designated Asian subcategories will not be summarized as combinations with other categories.• In addition, the standard race categories collected per IDSL will be summarized along with categories for mixed race. The categories are:
1. African American/African Heritage2. American Indian or Alaska Native3. Asian - Central/South Asian Heritage4. Asian – East Asian Heritage5. Asian – Japanese Heritage6. Asian – South East Asian Heritage7. Asian – Mixed Race8. Native Hawaiian or other Pacific Islander9. White – Arabic/North African Heritage10. White – White/Caucasian/European Heritage11. White – Mixed Race12. Mixed Race• "Asian – Mixed Race" is only used if more than one Asian category is selected, but no non-Asian races. Similarly, "White – Mixed Race" is only used if both of the White categories are selected, and no non-White races. If multiple races of different types are selected, then the overall "Mixed Race" category is used.• A participant will only be represented in a single category. A participant who selects a combination of races will be counted as "Asian – Mixed Race," "White – Mixed Race," or "Mixed Race," but not in each of the constituent terms. Therefore, the counts will add up to the total number of participants with a response, and the percentages will add to 100%.

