4.4. Justification for Dose and Washout Period

The dose level of 3mg/kg, the 2-week testing duration of each study period, the wash out period of at least 4 weeks, the IV route of administration and the post dose assessment times of Day 1, Day 2, Day 8 and Day 15 are selected for the PainCart study based on:

The dose by IV route is equivalent to the dose of 240mg SC proposed to be administered in an on-going repeat dose study in osteoarthritis patients (207804) and was administered in a healthy participant cohort in that study (3 mg/kg IV). Serum levels of total (complexed, free and partially complexed) GSK3858279 are below the lower limit of quantification (LLQ; 100 ng/mL) after 8 weeks following IV infusion at 3 mg/kg; based on data from a fully validated non-neutralising anti-idiotype capture (NNAIC) assay [GlaxoSmithKline Document Number [2020N429762_00](#)].

- Unbound CCL17 levels in serum have returned to approximately 30% of baseline at 4 weeks post dose.
 - A simulation plan was designed in order to investigate whether the statistical modelling for the PainCart assessments could control the potential properties of carry over effect. The plan details simulating carry over by varying different levels of drug accumulation in to the subsequent period, and the number of days it took for the drug to be eliminated. The results from the simulation showed even in the most extreme scenario (40% accumulation, 2 weeks reduction) the model was capable of extracting the treatment differences while controlling any potential carry over effects.
 - Given the statistical model chosen for analysis, and no increase in risk of safety, the washout period of at least 4 weeks is selected and still considered sufficient (data on file).
- Target engagement (percentage reduction from baseline of free CCL17) is above 90% within 24 hours of dosing IV and continues to 1-week post IV dose of 3 mg/kg. TE falls to 75% after 2 weeks post dose IV.
- t_{max} is at end of IV dose administration allowing PainCart testing to be scheduled at consistent fixed timepoints relative to dosing.

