6.1. Study Intervention(s) Administered

ARM Name	Active	Placebo
Intervention Name	GSK3858279	Placebo
Type	Biologic	Placebo
Dose Formulation	Solution for injection. GSK3858279 is formulated in 0.79 mg/mL sodium acetate, 50 mg/mL Sorbitol, 0.4 mg/mL polysorbate 20, glacial acetic acid 0.28 mg/mL, water for injection, pH 5.0. GSK3858279 contains no preservative.	Solution for injection. Normal Saline (0.9% sodium chloride)
Unit Dose Strength	50 mg/mL. Each vial has an extractable volume of 3.0 mL (150 mg per vial).	0.9% w/v sodium chloride, placebo level variable.
Dosage Levels	3 mg/kg. Single dose, once per study period.	Single dose, once per study period.
Route of Administration	IV Infusion	IV Infusion
Dosing Instructions	GSK3858279 will be infused over 1 hour. GSK3858279 can be diluted in normal saline prior to administration	The appropriate volume of placebo will be infused over 1 hour.
Use	Experimental	Placebo-control
IMP and NIMP	IMP	Placebo
Sourcing	Study medication is supplied by GSK.	Provided locally by the trial site, subsidiary, or designee.

Packaging and Labelling	Bulk supplies will be provided in a vial contained within a carton. Each vial and carton will be labelled as required per country requirement. Dispensed medication will be labelled as required per country requirement.	Commercial presentation. Dispensed placebo will be labelled as required per country requirement.
--------------------------------	---	--

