1.1. Version History

RAP Version	Approval Date	Protocol Version (Date) on which RAP is Based	Change	Rationale
Original RAP	01-July-2021	TMF-13778634 (25-May-2021)	None	Original Version

RAP Version	Approval Date	Protocol Version (Date) on which RAP is Based	Change	Rationale
RAP Amendment 1	##-October-2021	TMF-13778634 (25-May-2021)	
CPM Summary measure updated.
 
Definition of Exposure updated.
 
Reduced number of SAC displays.
 
Removal of the Bayesian PainCart by Day sensitivity analyses.
 
Inclusion of an All Analysis Complete (AAC) Milestone for exploratory endpoints.
	
Display is not analysed on the log scale, ratio to baseline is not suitable so change from baseline will be the summary measure.
 
The volume of infusion will be presented to calculate exposure to study drug, along with start and stop date/time as a single dose study.
 
Study has been terminated due to not meeting the futility threshold. A reduced SAC has been incorporated.
 
The reduced SAC includes the removal of the Bayesian PainCart by Day sensitivity analyses. Due to the complex modelling structure in PROC MCMC, the low number of subjects compared to the amount of parameters, and that summary statistics and figures will be able to demonstrate the Period and Day effects, the analyses were removed.
 
The AAC milestone has been incorporated to allow time for the analysis of all TLFs and not jeopardise the upper quartile performance targets and to report out the primary endpoints and AEs in a timely manner (SAC). This is due to the study terminating early and reporting the study 4 months ahead of the original SAC date.

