5. CONSIDERATIONS FOR DATA ANALYSES AND DATA HANDLING CONVENTIONS

5.1. Study Treatment & Sub-group Display Descriptors

Treatment Group Descriptions			
RandAll NG		Data Displays for Reporting	
Code	Description	Description	Order in TLF
A	3 mg/kg IV GSK3858279	GSK3858279	2
P	Placebo	Placebo	1

Treatment comparisons will be displayed as follows using the descriptors as specified:

1. GSK3858279 vs Placebo

For treatment sequence displays:

Treatment Group Descriptions			
RandAll NG		Data Displays for Reporting	
Code	Description	Description	Order in TLF
A/P/P	3 mg/kg IV GSK3858279 – Placebo – Placebo	GSK3858279-Placebo-Placebo	2
P/A/A	Placebo – 3 mg/kg IV GSK3858279 – 3 mg/kg IV GSK3858279	Placebo- GSK3858279- GSK3858279	1
		Total	3

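### The SAP's days-of-exposure formula ignores which infusions were GSK3858279 and adds an unexplained 90 days, so one-dose and two-dose participants can get the same figure

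*SAP*

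**What the plan says.** SAP 12.6.2 (Extent of Exposure) makes three statements.

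- On what is recorded: "This is a single dose per period study, the volume of infusion will be recorded, as will the start and stop date/time of infusion".
- On the derivation: "Number of days of exposure to study drug will be calculated based on the formula", followed by "Duration of Exposure in Days = Date of Subsequent/Last Dose – (Date of First Dose) +1+ 18*5".
- On undosed participants: "Participants who were randomized but did not report a treatment start date will be categorised as having zero days of exposure".

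The box does not say whether a dose means any infusion or only GSK3858279. It does not say whether the result is per participant or per period, or what 18 × 5 stands for.

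SAP 5.1 shows two sequences. One is "3 mg/kg IV GSK3858279 – Placebo – Placebo" (A/P/P, one active dose). The other is its mirror image, P/A/A, with placebo in Period 1 and two active doses after it.

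The SAP 1.1 entry for RAP Amendment 1 gives the reason for the updated exposure definition: "The volume of infusion will be presented to calculate exposure to study drug". Protocol 6.1 adds that "GSK3858279 can be diluted in normal saline prior to administration". Protocol 4.4 reports, for 3 mg/kg IV, that "Serum levels of total (complexed, free and partially complexed) GSK3858279 are below the lower limit of quantification (LLQ; 100 ng/mL) after 8 weeks".

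**The concern.** In a crossover where every completer receives both treatments, the date of the last infusion says little about drug exposure unless the formula also asks what was infused. This one does not. For A/P/P the last infusion is saline, so the 90 days are added after a placebo dose given eight weeks or more after the only active one. For P/A/A the clock starts at a placebo infusion, four weeks or more before any GSK3858279.

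The amended measure does not settle the matter. The days formula is still an instruction in the current text, and infusion volume alone does not give the dose, because GSK3858279 may be diluted and placebo has a volume too.

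At stake is whether the exposure listing, read as context for the safety data, correctly describes who had how much drug and for how long. As drafted, two programmers could produce different figures from the same dates.

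**Working it through.** The documents state no resulting exposure duration, so there is no figure to reproduce. The check applies the formula to planned dose dates.

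**Inputs**
- Tail: 18 × 5 = 90 days (SAP 12.6.2).
- Dose spacing: at least 4 weeks between Day 1 of successive periods (SAP 2.3). With 28 days, doses fall on days 1, 29 and 57. Spacings of 35 and 42 days are used as a range.
- Sequences: A/P/P and P/A/A (SAP 5.1).

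**Reading 1: one span per participant, any infusion**
- Both sequences: 57 − 1 + 1 + 90 = 147 days.

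**Reading 2: one span per participant, GSK3858279 infusions only**
- A/P/P: 1 − 1 + 1 + 90 = 91 days.
- P/A/A: 57 − 29 + 1 + 90 = 119 days.
- Reading 1 exceeds these by 147 − 91 = 56 days and 147 − 119 = 28 days.

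| Spacing (days) | Reading 1, both sequences | Reading 2, A/P/P | Reading 2, P/A/A |
|---|---|---|---|
| 28 | 147 | 91 | 119 |
| 35 | 161 | 91 | 126 |
| 42 | 175 | 91 | 133 |

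**Withdrawal after Period 1, sequence P/A/A**
- First and last dose coincide: 0 + 1 + 90 = 91 days, with only placebo given. The zero-day rule does not apply, because there is a treatment start date.
- A/P/P completers under Reading 2 also get 91 days, after a real active dose.

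**Reading 3: by period, using the subsequent dose date**
- Periods 1 and 2: 29 − 1 + 1 + 90 = 119 days each. Period 3: 1 + 90 = 91 days.
- If summed: 119 + 119 + 91 = 329 days, against 147 calendar days covered. The overlap is 329 − 147 = 182 days.
- If kept by treatment: A/P/P has 119 active and 119 + 91 = 210 placebo days; P/A/A has 210 active and 119 placebo days. The sequences then differ.

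**The tail against other time points**
- Protocol 4.4 has total drug below quantification after 8 weeks (56 days). The tail is 90 − 56 = 34 days longer.
- Final follow-up is 56 ± 4 days after the last dose (schedule of activities). At 28-day spacing that is day 57 + 56 = 113, give or take 4, while Reading 1 runs to day 147, nominally 34 days later.

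**The case against.** **The term is study drug, not GSK3858279.** The SAP leaves it undefined, and the protocol's nearest definition, study intervention, includes placebo (Protocol 6). A reader might infer that the SAP declares placebo days to be GSK3858279 exposure; it does not. This stands, but it does not rescue the formula. If placebo is included, the result cannot show how much active drug was given, and 90 days follow a saline infusion. If placebo is excluded, the dates must be limited to active infusions, and the text does not say so.

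**Double counting is not instructed.** A reader might infer that periods are double counted. That needs by-period values that are then summed, which the SAP never asks for. Nor does it arise in the single-span reading that makes the two sequences equal at 147 days. The supported point is that the level of calculation is undefined. SAP 6.1 refers exposure to GSK Core Data Standards, which are not available here and might settle it.

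**Little depends on it.** A reader might take this figure as the denominator for the safety results. The adverse event tables count participants and occurrences by period or treatment, with no person-time. Exposure appears only in Listing 15; there is no exposure summary table. The PainCart model does not use it, and the PK/PD figures use serum data. Listing 6 shows planned and actual treatments, so one-dose and two-dose participants can be told apart there. All of this stands and limits the consequence.

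**The tail is not shown to be wrong.** It is tempting to read 18 × 5 as five half-lives of 18 days and test that against the 8-week figure. Neither document gives that half-life, and the test would need an assumed body weight, distribution volume and log-linear decline. A fixed tail is also a different quantity from time to below quantification. The documents support only that the 90 days are unexplained and longer than 8 weeks.

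**Volume may be enough.** The dose is fixed at 3 mg/kg on screening weight, so the planned amount can be derived. That is true of the planned dose, but volume alone does not show the dose actually given.

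**Conclusion.** The point holds as a defect in a stated derivation. At 28-day spacing, with one span per dosed participant, A/P/P and P/A/A both get 147 days, against 91 and 119 days when only GSK3858279 infusions count. A participant given only placebo in Period 1 and then withdrawn gets 91 days. Equality between the sequences persists at 35- and 42-day spacing (161 and 175 days).

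These figures assume planned spacing and the two sequences shown in SAP 5.1. The 91 and 119 days keep the SAP's own 90-day tail, so they show the effect of ignoring treatment and do not endorse the tail. The 329-day sum is conditional on a by-period reading that the text leaves open but does not direct. The consequence is confined to the extent-of-exposure data, which serve as context for safety; no efficacy result or adverse event count changes.

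**What to change.** In SAP 12.6.2, do one of the following:

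- calculate drug exposure per participant from GSK3858279 infusion dates only: last minus first GSK3858279 dose date, plus 1, plus one tail, with zero days for anyone who received only placebo; or
- delete the days formula, since Amendment 1 already turns to infusion data.

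In either case, list the number of GSK3858279 and placebo infusions and the GSK3858279 dose given, by period, alongside infusion volume. If the tail is kept, state what 18 × 5 represents and reconcile it with the 8-week figure in Protocol 4.4.

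The cost is a wording change and a small programming change to the exposure derivation and Listing 15. Treatment, infusion times and screening weight are already planned data. If the formula is kept on active infusions only, the reported exposure becomes shorter.
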